8.1.2 SERIOUS ADVERSE EVENT (SAE)

An SAE is defined as an AE that meets any of the following criteria: Fatal or life-threatening*; requires or prolongs in-subject hospitalization**; results in persistent or significant disability/incapacity; congenital anomaly/birth defect; important medical event. An event's severity grading, action(s) taken, relationship to the hemodialysis or study procedure, and the outcome will all be used for SAE's.

*Life-threatening is defined as an event in which the subject was at risk of death at the time of the event. It does not refer to an event that hypothetically may have caused death if it was more severe.

**In-subject hospitalization is defined as an event in which the subject was admitted to the hospital for one or more days, even if released on the same day or an emergency room visit, which results in admission to the hospital. Emergency room visits that do not result in admission to the hospital should be evaluated for one of the other serious outcomes criteria.

8.1.3 UNANTICIPATED ADVERSE DEVICE EFFECT (UADE)

An unanticipated adverse device effect is defined by 21 CFR 812.3 as any serious adverse effect on the health of safety or life-threatening problem or death caused by or associated with, a device, if that effect, problem, or death was not previously identified in nature, severity, or degree of incidence in the investigational plan or application (including supplementary plan or application, or any other unanticipated serious problem associated with the device that relates to the rights, safety, or welfare of subjects. The Investigator or designee will indicate if they believe an event was an unanticipated adverse device effect on the case report form, and the Sponsor will evaluate for reporting requirements defined below.

8.2 SAFETY REPORTING

Safety reporting begins at the time of signed Informed Consent and ends at subject study completion.

Investigators shall submit to the Sponsor a report of any AE's or SAE's that occur during the study within five (5) working days but no later than ten (10) days after the Investigator learns of the event.

Investigators shall submit to the Sponsor and to the reviewing IRB a report of any UADE(s) that occur during the study as soon as possible but no later than five (5) working days after the Investigator learns of the effect. Sponsors will evaluate UADE's.

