5 STUDY PROCEDURES

Figure 1: Study Procedure Overview

ENROLLMENT

- Consent
- Inclusion/ exclusion criteria
- Demographics and medical history

STUDY PROCEDURE X3

- Prepare the device and subject [Subject ID ##-XX]
- Start monitoring session [wait 5+ minutes]
 - start hemodialysis procedure
- _____
- Continue monitoring post-procedure [10+ minutes] then STOP session
- Document adverse events and protocol devations
- Disconnect the subject and discard electrodes
- Repeat CM-1500 monitoring next 2 subsequent hemodialysis sessions (3 total)
- Subject participation is complete

CONFIDENTIAL Page 11 of 24

SPONSOR: ZMS

PROTOCOL: ZMS-1500-2021-Dialysis

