5.3.3 CM-1500 MONITORING SESSION

The Investigator or designated study personnel will operate the device by referencing the Instructions for Use (IFU) manual and following the study-specific steps outlined below.

- S16. Start the monitoring session by pressing "START" on the CM-1500 display monitor/monitoring screen. A message will appear informing the user that the monitoring session is in progress and the patient's baseline is being established. The device will begin to measure all five (5) parameters.
- S17. As monitoring continues, the display will show ECG and PPG pulse waveforms along with the Relative Index graph over time. Baseline measurements, for all parameters, are taken at the beginning of the monitoring session

 The subject should be relaxed during baseline establishment. The subject should remain in a supine or sitting position. The baseline measurement will continue for a minimum of 5 minutes.
- S19. Continue the monitoring session during the hemodialysis session. Upon completion of the session,

 continue the monitoring for a minimum of ten (10) minutes.

 If the subject needs to move to a different location during the 10-minute post-hemodialysis monitoring period, the time of movement should be noted on the CRF.
- S20. After the observation period has passed, "STOP" shall be pressed to end the monitoring session. The user will need to press "Yes" on the confirmation window to stop the monitoring session after pressing "STOP".
- S21. Document any observations or adverse events that occur throughout the entirety of the monitoring session.
- S22. After the monitoring session is stopped, remove the electrode array sets from the subject and dispose of the electrodes and wrist strap per site guidelines. Wipe down wrist cuff and cables per the IFU for next subject use.

SPONSOR: ZMS

PROTOCOL: ZMS-1500-2021-Dialysis

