5.4 REPEAT STUDY PROCEDURES AND STUDY COMPLETION

Subjects will continue to be monitored at each of their next two (2) subsequent hemodialysis sessions. If the device is not available or the subject is unable to complete the monitoring session at the following hemodialysis session, the next available hemodialysis session will be acceptable, and the date of the last procedure and number of hemodialysis sessions in between monitoring sessions will be captured on the case report form. All attempts should be made to complete the subject's participation in the study within two (2) weeks of enrollment.

For the remaining two monitoring sessions, the procedure will continue the same as previously performed. After the third CM-1500 monitoring session is complete, the subject's participation in the study is considered complete. If the subject elects to withdraw from the study before completing their third monitoring session, or if 30 days have passed since the initial monitoring session, subject withdrawal will be captured on the case report form. Additional subjects will be enrolled (up to 20) until 15 complete data sets of three (3) monitoring sessions each have been complete.

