5.5 ADVERSE EVENTS

Adverse Events (AE), Serious Adverse Events (SAE), or Unanticipated Adverse Device Effect (UADE) that occur after informed consent and before completion of the study will be recorded. SAE's may require follow-up contact via a telephone call, depending on the nature of the SAE.

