7 RISKS & BENEFITS

7.1 RISK DETERMINITATION & REDUCTION

This study is determined to be exempt and non-significant risk. An Investigational Device Exemption will not be submitted based on this determination.

Study subjects are subject to risk no greater than or similar to risks associated with undergoing a hemodialysis procedure. The study device and use of the device do not meet the definition of significant risk under 21CRF 812.3 (m). All adverse events will be recorded and analyzed to evaluate their significance. Possible risks may include:

- [Possible, Rare] Skin irritation or discomfort could occur from the electrodes
- [Possible, Mild] Discomfort could occur due to lying in a supine position for duration of the hemodialysis procedure.

Every possible effort will be made to reduce the risks to a minimum. Investigators or qualified designated study personnel will be experienced and skilled in performing hemodialysis procedures, receive training on the protocol and use of the device. All adverse events will be documented and reported to the Sponsor.

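### Skin reactions to the electrodes may be under-recorded: adverse events are documented before the electrodes come off, and non-serious reactions appearing after session 3 fall outside the window

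*Combined protocol and SAP*

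**What the plan says.** Section 7.1 lists two possible risks. One is tied to the electrodes and labelled rare: "Skin irritation or discomfort could occur from the electrodes". The other is discomfort from lying supine.

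In section 5.3.3, S20 ends the monitoring session when STOP is pressed. S21 then reads "Document any observations or adverse events that occur throughout the entirety of the monitoring session", and S22 follows with "After the monitoring session is stopped, remove the electrode array sets from the subject". Figure 1 has the same order: "Document adverse events and protocol devations", then "Disconnect the subject and discard electrodes". Neither place asks for an inspection of the skin once the arrays are off.

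Three sections set the recording window:

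- Section 5.5: adverse events "that occur after informed consent and before completion of the study will be recorded".
- Section 8.2: "Safety reporting begins at the time of signed Informed Consent and ends at subject study completion".
- Section 5.4: "After the third CM-1500 monitoring session is complete, the subject's participation in the study is considered complete".

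Section 5.5 foresees a possible follow-up telephone call for serious adverse events only. Section 8 rests the safety assessment on a review and summary of the recorded events.

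**The concern.** The arrays are adhesive and cover skin at the wrist and at the base of the neck and shoulder (S10 and S11). They stay on for at least 5 minutes before dialysis, through the whole treatment, and at least 10 minutes after it. Irritation under an array may first become visible when it is lifted, or later. The plan asks for adverse events just before that moment. After session 3 it then closes the record at about the same time.

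At stake is the completeness of the safety summary. Section 7.1 undertakes to record and analyse all adverse events, and section 9.1 says the results will inform whether a powered study can be defined. With about 15 subjects and a risk labelled rare, one missed event can be the difference between a table showing a skin reaction and one showing none.

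**Working it through.** The documents give no skin-reaction rate, so there is no figure of theirs to reproduce. The check has three parts.

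**1. When the window closes, section by section**

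| Source | Order of events |
|---|---|
| Section 5.3.3, S20 to S22 | STOP ends the session; adverse events documented; electrodes removed |
| Section 5.4 | Participation complete when the third session is complete |
| Figure 1 | Adverse events documented; subject disconnected; procedure repeated; participation complete |

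S20 read with section 5.4 puts completion at STOP, before removal. Figure 1 puts it after disconnection. The two cannot both define the end of the window in sections 5.5 and 8.2. On either reading, a reaction that appears after the subject has left session 3 is outside it.

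After sessions 1 and 2 the window in section 5.5 is still open, so a reaction can be recorded up to and including the next session. No step prompts for it.

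**2. Exposure among completers**

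Inputs: 15 complete data sets of three sessions each (section 5.4).

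- Applications planned: 15 × 3 = 45.
- Followed by an open window (sessions 1 and 2): 15 × 2 = 30.
- Little or no window after removal (session 3): 15, and 15/45 = 33%.

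Applications in subjects who start but do not complete are not in this count.

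**3. Size of a possible loss**

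Let f be the share of all skin reactions that first show at or after removal. Assume that reactions are equally likely at each session, that all of those after sessions 1 and 2 are reported, and that no delayed reaction is captured at session 3. Then

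share lost = f × 15/45 = f/3.

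| f (assumed) | Share of all skin reactions lost |
|---|---|
| 1 | 33% |
| 0.5 | 17% |
| 0.25 | 8% |

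For counts, let p be an assumed probability of a delayed reaction per application, with applications independent. Expected events are 45p if every application is followed up and 30p if only sessions 1 and 2 are. The chance of at least one is 1 − (1 − p)^n with n = 45 or n = 30.

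| p (assumed) | Expected, n = 30 | Expected, n = 45 | Difference | At least one, n = 30 | At least one, n = 45 |
|---|---|---|---|---|---|
| 1% | 0.30 | 0.45 | 0.15 | 26.0% | 36.4% |
| 2% | 0.60 | 0.90 | 0.30 | 45.5% | 59.7% |
| 5% | 1.50 | 2.25 | 0.75 | 78.5% | 90.1% |
| 10% | 3.00 | 4.50 | 1.50 | 95.8% | 99.1% |

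If reactions between sessions go unreported for want of a prompt, the loss exceeds f/3. The documents give no basis for putting a figure on that.

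**The case against.** The strongest reply is that the order of S21 and S22 is not the recording rule. Section 5.5 requires any adverse event between consent and completion to be recorded, so staff who lift an array and see a rash may record it. S22 is the last step of the section titled as the monitoring session, and Figure 1 places completion after disconnection. On that reading, a reaction visible at removal is inside the window at all three sessions, and only one that appears after the subject leaves session 3 is lost. The listed risk also includes discomfort, which a subject can report with the arrays on. The device is FDA-cleared, the risk is labelled rare, neither objective concerns safety, and no skin-reaction rate is a planned estimate.

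Most of this stands. A reader might infer that the step order bars recording at removal; section 5.5 shows that it does not. A reader might also infer that skin reactions are in fact under-counted, or that a third of them are lost. The documents do not support that either: they give no rate and no share of delayed reactions.

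Three things remain. No step asks anyone to look at the uncovered skin, the sections disagree on whether completion precedes removal, and on every reading a non-serious reaction arising after session 3 is excluded by a stated rule.

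**Conclusion.** The point holds in a limited form. Electrode skin reactions may be under-recorded: for lack of a window after session 3, and possibly for lack of a prompt after sessions 1 and 2. Up to 33% of planned applications among completers have little or no observation after removal.

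One third of all skin reactions is the ceiling on the loss only if everything after sessions 1 and 2 is reported. It also needs every reaction to be delayed and none to be captured at session 3. With half or a quarter delayed it is about 17% or 8%. If removal falls inside the window, the share that counts as delayed shrinks to reactions appearing after departure. At assumed rates of 1% to 10% per application, the expected shortfall is 0.15 to 1.5 events among 15 completers.

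Two further inferences should be avoided. Irritation is the only listed risk tied to the electrodes, but section 7.1 does not rank its two risks, so it should not be called the main one. The Relative Index analyses are not touched; the effect is confined to the completeness of the descriptive safety summary.

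**What to change.** 1. In section 5.3.3 and Figure 1, place adverse event documentation after electrode removal and add a look at the wrist and neck/shoulder electrode sites.
2. Reconcile S20, section 5.4 and Figure 1 by stating that completion of a session, and of participation, follows removal.
3. In sections 5.5 and 8.2, end the adverse event window with one adverse event question at the subject's next routine hemodialysis visit after session 3, and define that end point separately from the last monitoring session. State how the window closes if the subject does not attend.
4. Asking the same question at the start of sessions 2 and 3 would supply the prompt now missing between sessions.

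The cost is small: two steps reordered, a brief look at the skin, and a question at visits that take place anyway. The introduction notes that these patients often dialyse several times a week, so no study visit is added. All 45 applications would then have some observation after removal, against 30 now. The downside is a safety record that closes a few days later for each subject.

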9 STATISTICAL METHODS AND CONSIDERATIONS

9.1 SAMPLE SIZE DETERMINATION

This is a hypothesis generating study; therefore, hypothesis testing will not be performed. The sample size of 15 subjects is empirically determined to be sufficient for an early-phase pilot study characterizing the performance of the Relative Index during a hemodialysis procedure. The results of the study will be used to help the Sponsor determine if an appropriately powered clinical study can be defined.

9.2 ANALYSIS SET

All eligible subjects who were enrolled in the study and used the study device will be included in the analyses. Subjects who withdraw after enrollment and before device use will be excluded from the analyses.

9.3 DESCIPTIVE STATISTICS

Descriptive statistics will be calculated for all objectives and measures. Continuous variables will be summarized in terms of the mean, standard deviation (SD), median, quartiles, minimum, maximum and number of observations. Categorical variables will be summarized in terms of the number of subjects providing data, frequency count and percentage.

9.4 DEMOGRAPHIC AND BASELINE CHARACTERISTICS

All demographic and baseline variables collected at enrollment will be summarized using descriptive statistics.

SPONSOR: ZMS

PROTOCOL: ZMS-1500-2021-Dialysis

9.5 STATISTICAL ANALYSIS

The data for this study will be summarized using descriptive statistics. There is no formal hypothesis testing planned. Point estimates and the corresponding confidence intervals will be presented for the statistical analysis.

The primary evaluations pertaining to the performance of the CM-1500 device will examine the behavior the Relative Index value in accordance with subject outcomes and conditions that present during the hemodialysis sessions. Baseline performance of the CM-1500 device will be set in the Relative Index before the hemodialysis sessions. The primary analysis will utilize the descriptive statistics to characterize the changes in the CM-1500 Relative Index during the hemodialysis sessions, comparing to the baseline values. The analysis, however, can include investigation into individual vital sign parameters that the CM-1500 device (or another source) produces during a subject's session or 10-minute post-dialysis observation period.

The average of the Relative Index at baseline and each following hemodialysis sessions will be calculated first for the variability analysis. The inter-subject (between subject) and intra-subject (within-subject) variability in the Relative Index changes across multiple hemodialysis sessions will be estimated using the variance component analysis through a random effects model that includes only subject and hemodialysis session as random effects. The variance and % coefficient of variation (%CV) will be computed for the components of between-subject and within-subject through the model.

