2.3 STUDY DESIGN

The study is a prospective, single-arm, non-randomized, non-blinded, non-controlled, non-significant risk, single center study enrolling subjects consented to undergo a hemodialysis session as a part of their standard prescribed treatment plan. Subjects will consent to undergo non-invasive monitoring with the CM-1500 during three (3) separate hemodialysis sessions. Attempts will be made to have the monitoring sessions sequentially performed with their subsequently planned hemodialysis sessions. Up to 20 subjects will be consented and enrolled to ensure 15 subjects complete the study with the required number of monitoring sessions.

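### Does the unstated unit of analysis in Section 9.5 make the confidence interval for the primary Relative Index change too narrow?

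*Combined protocol and SAP*

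**What the plan says.** The design gives repeated measurements on few people. Section 2.3 states "Up to 20 subjects will be consented and enrolled to ensure 15 subjects complete the study with the required number of monitoring sessions", and Section 5.4 continues enrolment "until 15 complete data sets of three (3) monitoring sessions each have been complete". Section 9.2 adds that "All eligible subjects who were enrolled in the study and used the study device will be included in the analyses", so a subject may contribute one, two or three sessions.

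For the primary objective, Section 9.5 says "The primary analysis will utilize the descriptive statistics to characterize the changes in the CM-1500 Relative Index during the hemodialysis sessions", with baseline as the comparison. Section 9.3 lists the summaries for continuous variables: "mean, standard deviation (SD), median, quartiles, minimum, maximum and number of observations". That list has no confidence interval in it. Intervals appear only in a general sentence of Section 9.5: "Point estimates and the corresponding confidence intervals will be presented for the statistical analysis". No section gives the level, the method, or whether the unit is the subject, the session or the time point.

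Clustering is handled explicitly for the secondary objective only. There, Section 9.5 first averages the index and then fits a "random effects model that includes only subject and hemodialysis session as random effects". Section 9.1 describes 15 subjects as an empirical choice for a pilot without hypothesis tests, whose results will "help the Sponsor determine if an appropriately powered clinical study can be defined".

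**The concern.** Three sessions from one person are likely to resemble each other more than sessions from different people. A mean, SD and count taken over all sessions ignores this, and an interval built from them overstates the precision of the primary result. Section 9.3 reports a count of observations rather than of subjects for continuous variables, which makes a session-level calculation easy to imagine. The subject random effect is confined to the variability analysis, so nothing in the text carries it over to the primary estimate.

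Two analysts could therefore both comply with Section 9.5 and report intervals of clearly different width from the same data. The interval is the stated precision of the main finding, and the sponsor will use the study's results in judging whether a powered trial can be designed.

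**Working it through.** **No figure to reproduce.** The sample size of 15 is empirical; the plan states no precision target, SD or ICC.

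**Inputs from the documents.** n = 15 subjects and m = 3 sessions each (Sections 2.3 and 5.4), so N = 15 × 3 = 45 sessions.

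**Assumptions.** Two-sided 95% level; one change value per session; normal data; exchangeable sessions with intraclass correlation ρ from 0 to 0.7.

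**Formulas.**
- Design effect = 1 + (m − 1)ρ = 1 + 2ρ.
- Expected pooled variance = σ²[1 − 2ρ/(N − 1)] = σ²[1 − 2ρ/44].
- True SE / pooled SE = √{(1 + 2ρ) / (1 − 2ρ/44)}.

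At ρ = 0.3: √(1.6 / 0.9864) = 1.27. At ρ = 0.5: √(2.0 / 0.9773) = 1.43.

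**Simulation** (100,000 replicates per setting). The pooled interval uses 44 df (t = 2.015); the subject-mean interval uses 14 df (t = 2.145).

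| ρ | Design effect | True SE / pooled SE | Pooled coverage | Subject-mean coverage | Mean width, subject-mean / pooled |
|---|---|---|---|---|---|
| 0 | 1.0 | 1.00 | 95.0% | 95.0% | 1.05 |
| 0.1 | 1.2 | 1.10 | 92.7% | 95.1% | 1.16 |
| 0.3 | 1.6 | 1.27 | 87.9% | 95.1% | 1.34 |
| 0.5 | 2.0 | 1.43 | 83.1% | 95.1% | 1.51 |
| 0.7 | 2.4 | 1.57 | 78.5% | 95.0% | 1.67 |

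Unequal numbers of sessions change little. With 15 complete subjects and 5 with two sessions (45 + 10 = 55 sessions), pooled coverage is 95.2%, 92.8%, 88.3%, 84.5% and 80.0% at the same ρ values; the interval on 20 subject means stays between 94.9% and 95.3%.

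**Does the plan call for the pooled interval?** Three readings fit the text.
1. *Pool all sessions.* Possible, but stated nowhere.
2. *Summarise by session.* Section 5.3.1 gives each of the three sessions its own code, and Section 9.5 speaks of averages for each session, though for the variability analysis. Each summary then holds one value per subject, and an ordinary t interval keeps its level: 94.9% to 95.1% in simulation for ρ from 0 to 0.7.
3. *Summarise subject means.* This also holds its level, as the table shows.

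The interval sentence is general enough that it may be aimed partly or wholly at the variance components.

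**Is undercoverage certain under pooling?** No. Fixed differences between sessions inflate the pooled SD. At ρ = 0.3, shifts of −1, 0 and +1 SD bring pooled coverage to 95.5%; shifts of −0.25, 0 and +0.25 SD leave it at 88.7%.

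**Could a reader correct a pooled interval?** Yes, if the variance components refer to the same session value and there is no shared session effect. The SE of the mean is √(between/15 + within/45). With total variance 1 and ρ = 0.3 this is √(0.3/15 + 0.7/45) = 0.189. The pooled SE is about √(0.9864/45) = 0.148. The ratio is 1.27, as above.

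**The case for a change.** The strongest argument for a change is that the gap is real, concerns the primary result, and could be closed in a sentence or two with no new data. Fixing the unit beforehand would also stop it being chosen after the results are seen. Nothing suggests that text was blacked out here: Sections 9.2, 9.3 and 9.5 read as complete. At a moderate correlation the two intervals differ in width by a third to a half, which is not trivial.

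All of this stands as fact, but it shows an omission rather than an error. Calling pooling the natural reading goes further than the text allows, because the observation count in Section 9.3 does not settle the unit. The ICC is unknown. The index restarts at 100 in every session (Section 3.2), and nothing in the documents supports a high correlation of changes; at 0.1 the loss is about two percentage points.

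Nor is a subject-level interval a complete answer. If session is a random effect shared by all subjects and the target is a population of sessions, the subject-mean interval covers 90.0% at ρ = 0.3 when session variance is 5% of the remaining variance, and 85.3% at 10% (assumed values). If session is instead nested in subject with one value per session, the planned variability model is already a random-subject-intercept model, so the tool for a sound interval is in the plan.

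**Conclusion.** The omission exists, but no change follows. Section 9.5 leaves the unit, level and method of the primary interval open; it does not prescribe a wrong interval. Pooling would reduce a nominal 95% interval to about 93%, 88% and 83% coverage at ICC 0.1, 0.3 and 0.5. These figures assume the 95% level, one change value per session and no large session shifts, and they apply only if the analyst ignores a clustering that the same section already models. The other permitted readings hold 95% when no random session effect is common to all subjects.

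The consequences are limited in any case. No test, error rate or decision rule uses the interval. With three sessions for every subject, the point estimate is the same whether sessions are pooled or subject means are used. The between- and within-subject components will be reported, so the ICC can be recovered. For a pilot of this kind, the detail can be left to competent analysis.

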2 INVESTIGATIONAL PLAN

2.1 OBJECTIVES

The primary objective of the study is to characterize changes in the CM-1500 Relative Index during a hemodialysis procedure.

The secondary objective of the study is to characterize the intersubject and intrasubject variability in Relative Index changes across multiple hemodialysis sessions.

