5.3.1 PREPARING DEVICE FOR OPERATION

The Investigator or qualified designated study personnel will prepare the device for use by referencing the Instructions for Use (IFU) manual following the study-specific steps outlined below.

- S1. Complete the Unpacking, Inspection, and Accountability procedures and associated forms (refer to IFU for the full procedure).
- S2. Ensure the device is in a secure and stable location (refer to IFU for full procedure).
- S3. Connect the power supply cord to the display monitor and to an electrical outlet. The light will illuminate on the power adapter when it is connected to power.
- S4. Connect the CM-1500 wrist cuff trunk cable to the display monitor. The cable should double-click into the correct insertion position.
- S5. Connect the CM-1500 wrist cuff to the trunk cable. The cable should double-click into the correct insertion position.
- S6. Power on the device by pressing the external "ON/OFF" button located on the right side of the display monitor.
- S7. Press the "SETUP" button and select the desired user preferences, subject information (subject number), data storage mode, and device information. Press "SAVE" after all desired setup options are selected—the device will return to the Monitoring Screen.

CONFIDENTIAL Page 12 of 24

SPONSOR: ZMS

PROTOCOL: ZMS-1500-2021-Dialysis

- a. Select male/female
- Ensure the date/time of the CM-1500 aligns with the times that will be recorded in the
 post-treatment hemodialysis record from the hemodialysis machine and clinician
 watches
- c. Enter the subject ID as subject number (01-20) followed by AA, BB, or CC corresponding to session 1 (AA), 2 (BB), or 3 (CC). For example, the first subject, first session subject ID will be 01-AA and the next session will be 01-BB.
- S8. Insert a USB external storage drive (refer to "Data Storage Mode" in the IFU). The USB external storage drive should be labeled externally with the device serial number. The USB indicator icon should appear on the Monitoring Screen, signaling that the USB storage drive is connected and recognized.

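### Could Section 9.5 report a within-subject variance of zero because it does not say which model term is within-subject?

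*Combined protocol and SAP*

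**What the plan says.** Section 2.1 sets the secondary objective: to "characterize the intersubject and intrasubject variability in Relative Index changes across multiple hemodialysis sessions". Section 9.5 gives the method in three steps. Averages come first: "The average of the Relative Index at baseline and each following hemodialysis sessions will be calculated first for the variability analysis". The model is then "a random effects model that includes only subject and hemodialysis session as random effects". The output follows: "The variance and % coefficient of variation (%CV) will be computed for the components of between-subject and within-subject through the model". The residual is not mentioned, and neither is whether session is crossed with subject or nested in it.

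Section 5.3.1 labels each monitored session by subject number "followed by AA, BB, or CC corresponding to session 1 (AA), 2 (BB), or 3 (CC"). Section 5.4 fixes the amount of data: "Additional subjects will be enrolled (up to 20) until 15 complete data sets of three (3) monitoring sessions each have been complete". It also says that when a planned session cannot be monitored, "the next available hemodialysis session will be acceptable", with the number of sessions in between recorded on the case report form. Section 9.1 rules out hypothesis testing and says the results will "help the Sponsor determine if an appropriately powered clinical study can be defined".

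**The concern.** Two random effects are named and two components are reported, so a reader may pair them one to one: subject with between-subject, session with within-subject. Under crossed coding the second pairing is wrong. A crossed session effect is the shift that all subjects share at session 1, 2 or 3. It is estimated on 2 degrees of freedom. The spread of one subject's own values from session to session lies in the residual. Under nested coding with one value per session, session and residual cannot be separated at all.

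Intrasubject variability is half of the secondary objective. A reported value of 0 would say that the index change repeats perfectly from one dialysis session to the next, and that figure could enter the planning of a powered study.

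**Working it through.** The documents give no variance, precision or power figure, so there is none to reproduce. The check asks what each reading of within-subject would return.

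**Inputs.** From Section 5.4: 15 complete subjects, 3 sessions each. Assumed: one value per subject and session (suggested by the averaging step in 9.5), ANOVA or REML estimation (the plan names no method), and, for index-point figures only, a residual SD of 3.

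**Crossed session term alone.**

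- Estimate: max(0, (MS_session − MS_residual)/15). It is 0 when F = MS_session/MS_residual ≤ 1.
- Degrees of freedom: 3 − 1 = 2 and (15 − 1)(3 − 1) = 28.
- With no common shift, F follows F(2,28), so P(estimate = 0) = 1 − (28/30)^14 = 0.619, whatever the true SD.
- With 20 complete subjects: 1 − (38/40)^19 = 0.623. Under maximum likelihood with 15 subjects it would be about 0.76.
- With a common shift whose SD is r times the residual SD, F is inflated by 1 + 15r², so P(estimate = 0) = P[F(2,28) ≤ 1/(1 + 15r²)].

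| r | 1 + 15r² | P(session estimate = 0) |
|---|---|---|
| 0 | 1 | 0.62 |
| 0.25 | 1.9375 | 0.40 |
| 0.5 | 4.75 | 0.19 |
| 1 | 16 | 0.06 |

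**The three readings side by side.** Median estimated SD in index points at residual SD 3, with the 95% range in brackets (200,000 simulated data sets per row; the residual is MS_residual):

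| Shift SD | Session alone | Residual | Session + residual |
|---|---|---|---|
| 0 | 0 (0 to 1.27) | 2.96 (2.22 to 3.78) | 2.97 (2.24 to 3.75) |
| 1.5 | 1.18 | 2.96 | 3.27 |
| 3 | 2.46 | 2.96 | 3.91 |

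If the residual is pooled with session whenever the session estimate is truncated, its median in the first row is 2.93 instead of 2.96.

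**Why the sum does not depend on the coding.** With complete data, session + residual = (MS_session + 14 MS_residual)/15 = (2 MS_session + 28 MS_residual)/30. This is the within-subject mean square of a model with subject as the only random effect.

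**Nested coding.** In a simulated data set the REML log-likelihood was the same (−85.077062) for session/residual variance splits of 0/9, 1/8, 4.5/4.5, 8/1 and 8.9/0.1. Only the sum is determined, and the sum is the within-subject variance.

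**What the zero needs.** Three conditions must hold together: session coded as crossed, little or no common shift, and the session term reported as within-subject with the residual left out. Section 9.5 states none of them.

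**The case for a change.** The best case for a change is that the sentence does invite the wrong pairing, that the session labels support either coding, and that one line of text would settle the matter before data are seen. It is true that no other section defines the component, and that the residual and the sum part company when sessions share a shift (2.96 against 3.91 at shift SD 3). The denominator of the %CV is also unnamed.

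The stronger parts of the case do not carry. Within-subject variability already has a standard meaning, the spread of one subject's values across sessions, and an analyst who knows variance components would look for it in the residual or in session plus residual. A zero would stand beside 45 session values (15 x 3) that visibly differ, and Section 9.3 requires descriptive statistics for all objectives. Skipped dialysis sessions do not empty the session label of meaning: session 2 is the second monitored session, and the gap is recorded.

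Nor is one definition plainly better. Choosing the sum over the residual is a matter of preference and has a cost. A 30-df chi-square interval for the sum covers 95% only when there is no common shift; in simulation at residual SD 3, coverage fell to about 90% at shift SD 1.5 and 69% at shift SD 3. A 28-df interval for the residual stayed at 95%. Dividing the %CV by the mean change has no support in the documents.

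**Conclusion.** The gap is real but harmless as written: the plan leaves a definition unstated that an analyst would fill sensibly. The 62% is exact for 15 x 3 complete data with ANOVA or REML and no common shift, but it describes a misreading of Section 9.5, not its content. Under either conventional reading there is no pile-up at zero, and without a common shift the two medians differ by 0.01 index points at an assumed SD of 3 (by 0.04 if the residual is pooled on truncation). With a real shift they answer slightly different questions, and both are legitimate summaries.

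The component serves a descriptive secondary objective in a hypothesis-generating pilot, with no test, threshold or sample size resting on it. The analyst's report will have to say which term was used, and that is enough. The conclusion assumes one value per subject and session and an analyst who does not discard the residual.
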